5.4 Specimen Submission Criteria

- a. Patients must submit archival tissue (if available) for translational medicine as described in [Section 15.1](#). Patients must also be willing to undergo biopsies and submit tissue and blood for translational medicine as described in [Section 15.1](#).
- b. Patients must be offered the opportunity to participate in specimen banking of leftover tissue for future research as described in [Section 15.1b](#).

5.5 Regulatory Criteria

- a. Patients must be informed of the investigational nature of this study and must sign and give written informed consent in accordance with institutional and federal guidelines.

- b. As a part of the OPEN registration process (see [Section 13.4](#) for OPEN access instructions) the treating institution's identity is provided in order to ensure that the current (within 365 days) date of institutional review board approval for this study has been entered in the system.

6.0 STRATIFICATION FACTORS

There are no stratification factors for this study.

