4.0 STAGING CRITERIA

STAGE IIIC
Any T N3 M0

Stage IV
Any T Any N M1

Primary Tumor (T)

TX Primary tumor cannot be assessed (e.g., curettaged or severely regressed melanoma)
T0 No evidence of primary tumor
Tis Melanoma in situ
T1a Melanomas ≤1.0 mm in thickness without ulceration; mitosis <1/mm²
T1b Melanomas ≤1.0 mm in thickness with ulceration or mitoses ≥1/mm²
T2a Melanomas 1.01–2.0 mm in thickness without ulceration.
T2b Melanomas 1.01–2.0 mm in thickness with ulceration
T3a Melanomas 2.01–4.0 mm in thickness without ulceration
T3b Melanomas 2.01–4.0 mm in thickness with ulceration
T4a Melanomas >4.0 mm in thickness without ulceration
T4b Melanomas >4.0 mm in thickness with ulceration

Regional Lymph Nodes (N)

NX Patients in whom the regional nodes cannot be assessed (e.g., previously removed for another reason)
N0 No regional metastases detected
N1a 1 regional lymph node metastasis with micrometastasis^c
N1b 1 regional lymph node metastasis with macrometastasis^d
N2a 2–3 regional lymph node metastases with micrometastasis^c
N2b 2–3 regional lymph node metastases with macrometastasis^d
N2c In transit met(s)/satellite(s) without metastatic lymph nodes
N3 ≥4 regional lymph node metastases; or matted nodes; or in transit met(s)/satellite(s) with metastatic lymph node(s)

Distant Metastasis (M)

- M0 No detectable evidence of distant metastases
- M1a Metastases to skin, subcutaneous or distant lymph nodes and normal serum LDH
- M1b Metastases to lung and normal serum LDH
- M1c Metastases to all other visceral sites and normal serum LDH or distant metastases to any site combined with an elevated serum LDH

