5.3 Clinical/Laboratory Criteria

- a. Patients must be ≥ 18 years of age.
- b. Patients must have Zubrod Performance Status of ≤ 2 (see [Section 10.4](#)).
- c. Patients must have complete history and physical examination within 28 days prior to registration.
- d. Patients must have adequate hematologic function as evidenced by all of the following within 28 days prior to registration: absolute neutrophil count (ANC) $\geq 1,500/\text{mCL}$; hemoglobin $\geq 8 \text{ g/dL}$; and platelets $\geq 100,000/\text{mCL}$.
- e. Patients must have adequate hepatic function as evidenced by all of the following within 28 days prior to registration: total bilirubin $\leq 2.5 \times$ Institutional Upper Limit of Normal (IULN) (except patients with Gilbert's syndrome); and AST and ALT both $\leq 5 \times$ IULN.
- f. Patients must have adequate kidney function as evidenced by serum creatinine $\leq 2.0 \times$ IULN within 28 days prior to registration.
- g. Patients with a known history of HIV must have CD4 count \geq institutional lower limit of normal within 28 days prior to registration.
- h. Patients must not have known active Hepatitis B Virus (HBV) or Hepatitis C Virus (HCV) infection prior to registration.
- i. Patients must not have an active infection requiring systemic therapy at time of registration.
- j. Patients must not have organ allografts.
- k. Patients must not have received systemic treatment with corticosteroids ($> 10 \text{ mg}$ daily prednisone or equivalent) or other immunosuppressive medications within 14 days prior to registration. Inhaled or topical steroids, and adrenal replacement doses $\leq 10 \text{ mg}$ daily prednisone or equivalent are permitted in the absence of active autoimmune disease.

- l. Patients must not have a history of immune-mediated pneumonitis or colitis that required interruption of therapy or treatment of steroids.
- m. Patients with a known history of congestive heart failure (CHF), cardiomyopathy, myocarditis, myocardial infarction (MI), exposure to cardiotoxic medications, or with a clinical history suggestive of the above must have an EKG and Echocardiogram (ECHO) performed within 42 days prior to registration and as clinically indicated while on treatment.

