11.0 STATISTICAL CONSIDERATIONS

11.1 Accrual Goal

Although the primary objective aims to assess whether combination therapy ipilimumab and nivolumab is superior to single therapy ipilimumab in patients who have previously progressed on anti-PD-1 or anti-PD-L1 therapy, major additional objectives of this study include assessment of key biomarkers and genomic correlatives, particularly for patients who receive combination therapy. This study will use a design in which 63 patients will be randomized to receive combination therapy ipilimumab and nivolumab and 21 patients will be randomized to receive single therapy ipilimumab. Assuming an ineligibility rate of 10% the total accrual goal is 94 patients.

The unbalanced randomization is motivated by the necessity of evaluating the first secondary objective. In particular, the underlying rationale for the combination therapy is that initial progression on PD-1 blockade alone results from poor T cell recruitment. If the combination therapy is superior to single agent ipilimumab, evaluation of this hypothesis by comparing T cell infiltration between patients who have an objective response (confirmed and unconfirmed partial or complete response per RECIST 1.1) and patients who do not have an objective response to combination therapy will elucidate mechanisms that are imperative for design and development of further studies of combination therapy in this population. Thus, unbalanced randomization is necessary to ensure adequate sample size for evaluating this hypothesis. Assuming a response rate of 25% and 90% compliance in tissue and biopsy submission, then we anticipate accruing 14 eligible objective responders and 43 eligible objective non-responders in the combination therapy arm.

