11.2 Primary Analysis and Interim Analysis

For our primary objective, we will compare the PFS between arms using a log-rank test. Kaplan-Meier plots will be constructed and median PFS for each arm with corresponding 95% Brookmeyer-Crowley confidence intervals will be estimated.

Combination therapy will be considered superior to single therapy ipilimumab if median progression-free survival (PFS) is doubled. Based on Hodi et al., we assume the median PFS for patients randomized to single therapy ipilimumab to be 3 months such that the target alternative PFS for patients randomized to combination therapy is 6 months (corresponding to a hazard ratio of 0.5). We assume exponential survival, 24 months of accrual, 12 additional months of follow-up after the last patient is randomized, and that the final analysis will be conducted at the one-sided $\alpha = 10\%$ level. One interim analysis for futility will be performed after approximately 50% information under the null (corresponding to approximately 41 events across both arms which is expected to occur 16-17 months after accrual starts). If the hazard ratio favors the control arm (is greater than 1), the study will be stopped due to futility. Given the modest sample size, no plans for formal interim analysis of efficacy are included. Using simulations (10,000 replicates), this design has overall type I error of 9.0% and power of 89%. Under the null, the probability of stopping early for futility at the interim analysis is 50% and under the alternative, the probability of stopping early is 4.1%.

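### With 21 controls, no strata and an unadjusted log-rank test as the only PFS comparison, a chance prognostic imbalance can distort the realised result in either direction; an adjusted hazard ratio should be pre-specified

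*Combined protocol and SAP*

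**What the plan says.** Section 6.0 is one sentence: "There are no stratification factors for this study". Section 11.1 fixes the arms: "63 patients will be randomized to receive combination therapy ipilimumab and nivolumab and 21 patients will be randomized to receive single therapy ipilimumab".

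For the primary endpoint, Section 11.2 says "we will compare the PFS between arms using a log-rank test". It adds Kaplan-Meier plots and a median with a 95% interval for each arm. A hazard ratio appears there only as the design target (0.5) and in the futility rule (stop if above 1). No final treatment hazard ratio with an interval is planned, and neither strata nor covariates are named. The regression models in Appendix 18.1 concern response within each arm, not PFS.

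The population is mixed. Section 5.3b reads "Patients must have Zubrod Performance Status of" at most 2. Section 5.1 admits unresectable Stage III and Stage IV disease and treated CNS metastases. The Section 9 calendars require performance status before registration; stage and CNS history are needed to establish eligibility. LDH is different. In Section 4.0, M1c includes "distant metastases to any site combined with an elevated serum LDH", but no eligibility criterion and no calendar row requires an LDH test.

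**The concern.** In an arm of 21, each patient is nearly 5 percentage points (1/21 = 4.8%). If a factor that drives PFS falls unevenly, an unadjusted test attributes part of its effect to treatment, and the plan has no pre-specified analysis that would separate the two.

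Three things are at stake:

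- how far the single realised comparison can be trusted;
- power and the size of the hazard ratio, if a strong factor is ignored;
- credibility, because an imbalance noticed afterwards invites an adjusted analysis whose covariates were chosen with the results in view.

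**Working it through.** **Inputs from the documents.** 63 v 21 patients (11.1). From 11.2: control median PFS 3 months, exponential; target hazard ratio 0.5; 24 months' accrual plus 12 months' follow-up; one-sided 10% level; futility look at about 41 events.

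**Assumed, because the documents give neither.** Factor prevalence 30-50%; prognostic hazard ratio 1.5 to 2.5.

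**The plan's own figures.** Section 11.2 states power 89%, type I error 9.0%, and futility stops of 50% (null) and 4.1% (alternative). Schoenfeld's formula, Φ(ln 2 × √(0.25 × 0.75 × d) − 1.28), gives 91.5% at d = 78 events and 92.9% at d = 84. Simulating the documented design (10,000 trials) gives power 92.0%, type I error 11.3%, and stops of 49% and 2.3%. The stated figures therefore do not reproduce. A run with the allocation reversed (21 combination, 63 control) comes close: 88.4%, 8.7%, 51% and 4.0%. That is a separate matter for the sponsor to check. Here the reference is the simulated 92.0% and 11.3%.

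**Step 1: how large chance imbalance gets.** The SD of the between-arm difference in prevalence p is √(p(1−p)(1/21 + 1/63)).

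- p = 0.5: √(0.25 × 0.0635) = 12.6 points (10.9 with 42 v 42)
- p = 0.4: √(0.24 × 0.0635) = 12.3 points
- p = 0.3: √(0.21 × 0.0635) = 11.5 points (10.0 with 42 v 42)

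The chance of a difference of at least 20 points, both directions combined, is 11.5% (p = 0.5) and 8.5% (p = 0.3) by binomial. It is 12.9% and 10.0% with factor totals fixed at 42 and 25 of 84.

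**Step 2: what a fixed imbalance does.** One factor at 50% prevalence. Controls worse: 14/21 v 28/63 (66.7% v 44.4%, 22 points). Controls better: 7/21 v 35/63. There are 5,000 trials per cell, with the futility look included. Each cell shows controls worse / controls better.

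| Prognostic HR | False success, unadjusted | False success, stratified | Power at HR 0.5, unadjusted | Power at HR 0.5, stratified |
|---|---|---|---|---|
| 1.5 | 18.1% / 6.3% | 10.6% / 11.6% | 95.1% / 84.3% | 90.1% / 90.1% |
| 2.0 | 24.2% / 3.5% | 10.9% / 11.3% | 95.9% / 74.1% | 89.3% / 89.3% |
| 2.5 | 28.0% / 2.5% | 11.6% / 10.6% | 97.2% / 66.4% | 90.5% / 89.7% |

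With no treatment effect, the median unadjusted hazard ratio moves both ways: 0.90 / 1.08, 0.86 / 1.14 and 0.82 / 1.18. The futility look moves as well. At true hazard ratio 0.5 and prognostic hazard ratio 2, with controls better, it stops 7.0% of trials unadjusted against 3.2% stratified.

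**Step 3: average over randomisations.** Two factors at 40% prevalence, Cox Wald test, no interim look, true hazard ratio 0.5. Two sets of 3,000 trials.

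| Each factor's HR | Power, unadjusted | Power, adjusted | Difference (points) |
|---|---|---|---|
| 1.5 | 90.3%, 89.0% | 91.6%, 90.5% | +1.3, +1.5 |
| 2.0 | 84.7%, 85.4% | 90.6%, 91.6% | +5.9, +6.2 |
| not prognostic | 92.4%, 92.7% | 91.6%, 92.3% | −0.8, −0.4 |

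Each power has a simulation standard error of about √(0.9 × 0.1/3,000) = 0.5 points, so the first gain is best read as about 1-3 points. With only one factor (50% prevalence, stratified log-rank, look included) power is 90.4% v 90.5% at hazard ratio 1.5, 88.2% v 89.8% at 2.0, and 84.7% v 89.5% at 2.5.

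Averaged type I error of the unadjusted log-rank is 10.8-11.4%, against 11.3% with no factor present.

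**Step 4: where the attenuation comes from.** With two factors of hazard ratio 2, the mean estimated hazard ratio is 0.53 unadjusted and 0.48 adjusted (truth 0.50). Forcing both factors into perfect balance leaves 0.54 and 0.48, with power 87.3% v 91.1%. The attenuation, and most of the power gap, therefore come from leaving out a prognostic covariate and not from imbalance.

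**The case against.** An unadjusted log-rank test is a valid randomised comparison. A reader might infer from Step 2 that the plan is biased or has inflated type I error. Step 3 does not support that: averaged over randomisations the factor leaves type I error where it was, and imbalances as large as the one in Step 2 are uncommon. A reader might also infer that imbalance pulls the estimate toward the null. It does not; it shifts the estimate either way, and Step 4 shows the average attenuation has another cause.

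The benefit is also modest unless strong factors are assumed. At hazard ratio 1.5 the adjusted estimate is no nearer the truth (0.479, against 0.504 unadjusted). Section 2.0 itself says second-line data after PD-1 inhibitors are lacking, so prognostic strength here cannot be taken from the documents. M category cannot be presumed available, since it needs LDH. Choosing covariates late in a trial with 21 controls carries its own credibility cost.

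All of that stands. What remains is that the plan offers no adjusted analysis and no final hazard ratio with an interval, although at least one suitable baseline value, Zubrod status, must be assessed before registration.

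**Conclusion.** The concern holds as a conditional one. The unadjusted comparison can be distorted, in a direction nobody can predict, by the particular allocation obtained, and omitting a strong factor costs power and attenuates the hazard ratio. On the assumed values, a 22-point imbalance on one factor of hazard ratio 2 gives false success in about 25% or 3% of null trials, against about 10-11% when adjusted. The average power gain from an adjusted test is about 1-3 points (two factors of hazard ratio 1.5) to about 6 points (two of hazard ratio 2). It is smaller with a single factor of the same strength: 0.1 point at 1.5 and 1.6 points at 2.0.

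It would be wrong to infer that reporting an adjusted hazard ratio beside the log-rank test recovers this power. While the log-rank test decides, power stays at the unadjusted value, and only the effect estimate and its interval improve.

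**What to change.** Before results are seen, pre-specify as the reported treatment effect a Cox hazard ratio with confidence interval, adjusted for Zubrod status at registration (0 v 1-2), alongside the log-rank test. Stage or CNS-metastasis history may be added. Use M category only if it, or LDH, was actually recorded. With 21 controls, one or two covariates is the limit.

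State which result governs the conclusion if the two disagree. If the power gain is wanted, the adjusted or stratified test must be named as the primary test; otherwise the hazard ratio is for estimation only.

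The cost is SAP wording and one model on data already required. If the adjusted test is made primary and the factors prove not prognostic, up to about 1 point of power is lost. The pages are stamped closed, so adding strata to the randomisation is no longer a practical alternative.

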7.1 Pre-Medication and Concomitant Medications

a. Pre-Medication

Premedication associated with standard drug administration and supportive care (including anti-diarrheals, antibiotics, diuretics or other medications) may be given as indicated by the current American Society of Clinical Oncology (ASCO) guidelines. Premedication for the use of prophylaxis for infusion reactions (e.g., diphenhydramine, acetaminophen, or other medications) may be given per institutional standard.

For patients that experience infusion reactions the following prophylactic premedications are recommended for future infusions: diphenhydramine 50 mg (or equivalent) and/or acetaminophen/paracetamol 325 to 1000 mg at least 30 minutes before additional nivolumab or ipilimumab administrations.

As there is potential for hepatic toxicity with nivolumab or nivolumab/ipilimumab combination, drugs with a predisposition to hepatic toxicity should be used with caution in patients treated with nivolumab containing regimen.

b. Concomitant Medications

The following medications are prohibited during the study (unless utilized to treat a drug related adverse event):

- Immunosuppressive agents
- Immunosuppressive doses of systemic corticosteroids (e.g., prednisone >10 mg daily or equivalent)
- Any concurrent anti-neoplastic therapy (i.e., chemotherapy, hormonal therapy, immunotherapy, extensive, non-palliative radiation therapy, or standard or investigational agents for treatment of melanoma)

7.2 Treatment – Arm 1: Ipilimumab Alone

Patients will receive the following treatment until completion of 4 cycles of treatment or meeting one of the criteria in [Section 7.5](#).

Agent	Dose	Route	Day	Schedule*
Ipilimumab	3 mg/kg	IV over 90 mins	1	q 21 days for 4 cycles

* Note: 1 cycle = 21 days

7.3 Treatment – Arm 2: Ipilimumab + Nivolumab

Patients will receive the following treatment until meeting one of the criteria in [Section 7.5](#).

Cycles 1-4

Agent	Dose	Route	Day	Schedule*
Nivolumab	1 mg/kg	IV over 30 mins	1	q 21 days for 4 cycles only.
Ipilimumab**	3 mg/kg	IV over 90 mins	1	q 21 days for 4 cycles only

* Note: 1 cycle = 21 days

**Ipilimumab to start 30 minutes after the end of nivolumab infusion.

Cycles 5+

Agent	Dose	Route	Day
Nivolumab	480 mg	IV over 30 mins	1 of every cycle

Note: 1 cycle = 28 days

7.4 Full CDUS Reporting Requirement

Because this study contains an investigational drug for which CTEP holds the IND, it falls under CTEP requirements for full reporting. This involves required submission of cycle-specific toxicity and dose information (see [Section 14.4](#), the **S1616** Treatment Form, and the **S1616** Adverse Event Form).

A cycle is defined as:

- Arm 1: 21 days
- Arm 2: 21 days for first 4 cycles; 28 days for Cycles 5+

7.5 Criteria for Removal from Protocol Treatment

- Progression of disease as defined in [Section 10.2d](#). However, the patient may continue to stay on protocol treatment as long as, in the opinion of the treating investigator, the patient is continuing to clinically benefit from treatment. This may occur if there are lesions that continue to respond to the therapy despite others progressing, or if there is symptomatic relief of symptoms on therapy.

- b. Completion of 4 cycles on Arm 1.
- c. Symptomatic deterioration (as defined in [Section 10.2e](#)).
- d. Unacceptable toxicity (see also [Section 8.0](#)).
- e. Treatment delay for any reason > 12 weeks.
- f. The patient may withdraw from the study at any time for any reason.

7.6 Discontinuation of Treatment

All reasons for discontinuation of treatment must be documented in the Off Treatment Notice.

7.7 Follow-Up Period

All patients will be followed until death or 3 years after registration, whichever occurs first.

8.0 TOXICITIES TO BE MONITORED AND DOSE MODIFICATIONS

8.1 NCI Common Terminology Criteria for Adverse Events

Two different versions of the NCI Common Terminology Criteria for Adverse Events (CTCAE) will be used on this study.

a. Serious Adverse Event (SAE) reporting

The CTCAE (NCI Common Terminology Criteria for Adverse Events) Version 5.0 will be utilized **for SAE reporting only**. The CTCAE Version 5.0 can be downloaded from the CTEP home page (<https://ctep.cancer.gov>). All appropriate treatment areas should have access to a copy of the CTCAE Version 5.0.

b. Routine toxicity reporting

This study will utilize the CTCAE Version 4.0 for routine toxicity reporting. A copy of the CTCAE Version 4.0 can be downloaded from the CTEP home page (<https://ctep.cancer.gov>). All appropriate treatment areas should have access to a copy of the CTCAE Version 4.0.

8.2 General considerations

- a. No dose reductions are allowed.
- b. The maximum dose delay for any reason is 84 calendar days (12 weeks).
- c. Patients on IV steroids may be switched to an equivalent dose of oral corticosteroids (e.g., prednisone) at start of tapering or earlier, once sustained clinical improvement is observed. Lower bioavailability of oral corticosteroids should be taken into account when switching to the equivalent dose of oral corticosteroids.

8.3 Dose Delay Criteria Ipilimumab (Arm 1)

Dose modifications for ipilimumab by adverse event type are detailed in [Table 8.1](#). General considerations for dose modifications are as follows.

- a. It is necessary to avoid study drug dosing and initiate appropriate evaluation and/or treatment for the following adverse events:
- Any \geq Grade 3 skin related adverse event regardless of causality.
 - Any \geq Grade 2 non-skin related adverse event (including immune-mediated adverse reactions), except for easily corrected laboratory abnormalities that do not reflect underlying organ pathology.
 - Any \geq Grade 3 laboratory abnormality.
 - Any adverse event, laboratory abnormality or intercurrent illness that, in the opinion of the treating investigator, presents a substantial clinical risk to the patient with continued dosing.
 - It may be necessary to hold study drug to evaluate Grade 1 events that suggest ongoing or incipient autoimmune disease including GI toxicity, diarrhea, pancreatitis, hepatitis, pituitary insufficiency, early evidence of neurologic events, skin toxicity until diagnosis and progression are determined.
- b. Ipilimumab may be restarted if/when the adverse event(s) resolve(s) in severity or returns to baseline within 2 weeks of initial dose administration:
- If the adverse event has been determined not be related to ipilimumab or is not an autoimmune/inflammatory event. If more than 1 dose is to be skipped or > 2 week delay is expected due to current events not related to study the dosing schedule modifications must be discussed with the study chairs prior to implementation.
 - If the *adverse event has resolved to \leq Grade 1*, ipilimumab dosing may be restarted at the next scheduled timepoint per protocol. Please follow guidelines for specific events. Please note that re-initiating treatment may be associated with recurrence or exacerbation of autoimmune or inflammatory events. In some instances clinical resolution of events such as colitis may be associated with residual pathologic changes and should require evaluation of complete resolution prior to restarting therapy.
 - If the adverse event has not resolved in the protocol-specified dosing window (3 weeks [± 3 calendar days]), the next scheduled dose will be skipped and dosing will be resumed at the subsequently scheduled dose.
 - Events which require intervention with immunosuppressant therapy, steroids, surgery, or hormone replacement generally require permanently stopping study treatment.
- c. Permanently discontinue ipilimumab for any of the following:
- Persistent adverse reactions that require holding more than 2 treatment doses.
 - Any related Grade 3 or 4 event (see exceptions below)
 - Any event that requires immunosuppressive treatment or systemic steroids which cannot be discontinued during the time in which it takes to hold more than 2 treatment doses
 - Severe or life-threatening adverse reactions, including any of the following:
 - Colitis with abdominal pain, fever, ileus, or peritoneal signs; increase in stool frequency (7 or more over baseline), stool incontinence, need for IV hydration for more than 24 hours, gastrointestinal hemorrhage, and gastrointestinal perforation

- Aspartate aminotransferase (AST) or alanine aminotransferase (ALT) >5 times the upper limit of normal or total bilirubin >3 times the upper limit of normal
- Stevens-Johnson syndrome, toxic epidermal necrolysis, or rash complicated by full thickness dermal ulceration, or necrotic, bullous, or hemorrhagic manifestations
- Severe motor or sensory neuropathy, Guillain-Barré syndrome, or myasthenia gravis
- Severe immune-mediated reactions involving any organ system (e.g., nephritis, pneumonitis, pancreatitis, non-infectious myocarditis)
- Immune-mediated ocular disease that is unresponsive to topical immunosuppressive therapy
- Any adverse event, laboratory abnormality or intercurrent illness which, in the judgment of the investigator, presents organ specific injury and/or a substantial clinical risk to the patient with continued dosing.

NOTE: The following neurological adverse events require permanent discontinuation of ipilimumab and define unacceptable neurotoxicity:

- Any motor neurologic toxicity \geq Grade 3 regardless of causality
- Any \geq Grade 3 treatment related sensory neurologic toxicity

Please refer to [Appendix 18.3](#) and [Appendix 18.4](#) for specific treatment algorithms.

- d. Exceptions to Permanent Discontinuation of Ipilimumab
- Potentially reversible inflammation (< Grade 4), attributable to a local anti-tumor reaction and a potential therapeutic response. This includes inflammatory reactions at sites of tumor resections or in draining lymph nodes, or at sites suspicious for, but not diagnostic of metastasis.
 - Hospitalization for \leq Grade 2 adverse events where the primary reason for hospitalization is to expedite the clinical work-up.
 - Patients with the following conditions where in the treating investigator's opinion continuing study drug administration is justified based on the potential for continued clinical benefit:
 - Patients treated with systemic steroids for less than 2 weeks without evidence of autoimmune disease requiring steroids treatment
 - Grade 2 skin rash treated with topical steroids for less than 4 weeks
 - Grade 2 ocular toxicity that has completely responded to topical therapy within 4 weeks
 - Endocrinopathies where clinical symptoms are controlled with appropriate hormone replacement therapy. **Note:** Ipilimumab may not be restarted while the patient is being treated with systemic corticosteroids except for patients on stable doses of hormone replacement therapy such as hydrocortisone.
- e. Allowance for ipilimumab dose delay
- In general, patients who meet criteria to resume ipilimumab will also have met criteria to resume nivolumab with ipilimumab, so it should be feasible to synchronize dosing of both drugs when resuming ipilimumab. In order to facilitate this, the dosing calendar days of nivolumab and ipilimumab may be adjusted within a +/- 5 day window, as long as consecutive nivolumab doses are given at least 12 calendar days apart.
 - If an ipilimumab dose is delayed beyond 6 weeks from the prior ipilimumab dose, then subsequent nivolumab doses should be rescheduled to maintain at least a 3-week interval between consecutive ipilimumab doses.

- Dosing delays to manage drug-related adverse events, such as prolonged steroid tapers, are allowed. Disease assessments should continue as per protocol even if dosing is delayed.
- Dosing delays resulting in no ipilimumab dosing for > 6 weeks that occur for non-drug-related reasons may be allowed if approved by the Study Chairs. Disease assessments should continue as per protocol even if dosing is delayed.
- In event of any Grade 2 adverse event experienced while on combination nivolumab plus ipilimumab therapy, patient may resume treatment/may be continued on nivolumab monotherapy alone, at the discretion of the treating investigator
- Ipilimumab will not be given as monotherapy for Arm 2.

NOTE: If adverse events result in permanent discontinuation of ipilimumab, then subsequently manage dose delays under Management/Next Dose for nivolumab alone

